6.5.2 Handling and Storage of Trial Intervention

At the investigative site, IMP must be securely stored under conditions indicated in the IB; IMP accountability is the responsibility of the Investigator (Section 10.5).

Details on handling and storage of ASN51 (placebo) capsules are provided in the Study Reference Manual.

6.5.3 Accountability of Trial Intervention

The Investigator is responsible for ensuring IMP is stored in a secure limited access location at controlled temperature as described in the IB and according to product packaging. The storage facility must be available for inspection by the trial monitor at any time during the trial.

A drug accountability record must be maintained for all IMP received, dispensed, returned, and/or lost during the trial. This record must be kept current and made available to the trial monitor for inspection. Following the close-out of the trial, all unused IMP must be returned to Sponsor and/or its designee unless other instructions have been provided for final disposition of the IMP.

6.6 Participant Assignment, Randomization, and Blinding

6.6.1 Participant Assignment

Participants will be sequentially assigned an identification number upon signing of informed consent.

Once eligibility is confirmed, participants will be randomized via an Interactive Web Response System (IWRS). Randomization will be stratified as described in Section 4.2.

6.6.2 Blinding and Unblinding

The initial 24 weeks of intervention will be administered in a double-blind fashion. Participants, Investigators, site personnel, and the Sponsor and/or designees will be blinded to randomization assignment.

The statistician(s) responsible for generating the randomization schedule, and personnel responsible for preparing trial intervention supplies will be unblinded.

Randomization numbers will be assigned sequentially. Each participant will be dispensed blinded trial intervention (ASN51 or placebo), labeled with the participant's unique randomization number. Unblinding mechanisms will be available by IWRS.

Should any trial stopping criteria (Section 7.4) be triggered the involved participant(s) will be unblinded to randomization assignment by the SRC to determine if the event was related to IMP.

In the event of an emergency, the Investigator has the sole responsibility for determining if unblinding of a participant's randomization assignment is warranted. The safety of the participant will be the first consideration in making such a determination. If a participant's randomization assignment is unblinded, the Sponsor Medical Monitor must be notified within 24 hours.

Following completion of the 24-week DB Intervention Period, data will be unblinded after database lock for the purpose of data analysis; however, participants, Investigators, and study site staff will remain blinded to DB treatment assignment until the end of the 36-week LTE Period (end of the study).

6.6.3 Randomization

Participants will be randomized (1:1:1) to ASN51 at 1 of 2 dose levels, or placebo.

The randomization schedule will be computer generated by the Sponsor or designee. An IWRS will be used.

6.7 Trial Intervention Compliance

Site personnel will maintain a record of all IMP dispensed to each participant. Participants will also be instructed to bring all IMP containers (blister packs and/or unused capsules) to each clinic visit.

6.8 Concomitant Therapy

Investigators may prescribe any concomitant medications or treatments deemed necessary to provide adequate supportive care, except those specified as prohibited medications (Section 6.8.1).

6.8.1 Prohibited Concomitant Therapy

To be eligible for the trial, participants must not require chronic daily drug intake of the medications listed below. If participants discontinue any of these medications prior to randomization, a washout period of the lesser of 5 half-lives or 30 days is required.

The following medications will remain prohibited throughout the DB Intervention Period:

- Any investigational product intended for AD (e.g., anti-tau antisense oligonucleotide or gene therapy, active or passive anti-amyloid immunotherapy, active or passive anti-tau immunotherapy, O-GlcNAcase inhibitor, etc.) or other investigational product within 8 weeks prior to randomization
- Anticoagulants
- Moderate and strong inhibitors of CYP3A4 and CYP2C19 (refer to Appendix 16).

During the LTE Period, use of prohibited/restricted medications will be addressed on a case-bycase basis in consultation with the Sponsor Medical Monitor.

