5.4 Exclusion Criteria

An individual who meets any of the following criteria will be excluded from participation in this trial:

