5.4.3 Exclusion Criteria by Concomitant Medications/Prior Therapies

- 33. Initiation or change in dose of an acetylcholinesterase inhibitor and/or memantine within less than 8 weeks prior to randomization.
- 34. Positive urine drug test at Screening. Testing positive for benzodiazepines or opioids in urine drug testing is permitted if determined by the Investigator to be due to appropriate medical use and not drug abuse. Medical cannabidiol (CBD) use is permitted if prescribed by a medical provider in accordance with local laws and if in the opinion of the Investigator its use does not pose a risk to participant safety or compromise a participant's performance on cognitive assessments.
- 35. Taking medications known to prolong PR or QT intervals (e.g., calcium channel blockers or beta blockers) unless on a stable dose of (or titrating) within 12 weeks prior to randomization.
- 36. Use of any medications that, in the opinion of the Investigator, may contribute to cognitive impairment, put the participant at higher risk for AEs, or impair the participant's ability to perform cognitive testing or complete study procedures.

- 37. Any prior or ongoing exposure to active or passive anti-amyloid immunotherapy, anti-tau immunotherapy, an anti-tau antisense oligonucleotide or gene therapy, or O-GlcNAcase inhibitor.
- 38. If previously exposed to an investigational product other than active or passive anti-amyloid immunotherapy, anti-tau immunotherapy, an anti-tau antisense oligonucleotide or gene therapy, or O-GlcNAcase inhibitor, then 12 weeks or 5 half-lives (whichever is longer) must have passed prior to randomization.
- Known allergy to any components of the ASN51 formulation.
- 40. Requires use of anticoagulants during trial participation (to permit safe CSF collection).
- 41. Prior use of a moderate or strong inhibitor of CYP3A4 within a period of 5 half-lives of randomization (refer to Appendix 16).
- 42. Prior use of a moderate or strong inhibitor of CYP2C19 within a period of 5 half-lives of randomization (refer to Appendix 16).

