6.8.2 Permitted Concomitant Therapy

Concomitant therapy, particularly medications that could potentially affect cognition, should be maintained at stable doses throughout the trial, unless a change is medically necessary.

Medications (investigational, prescription, over the counter, and herbal) and nutritional supplements taken during the 30 days prior to Day 1 will be reviewed and recorded as prior medications.

All concomitant medications taken during the trial, and any changes since the previous visit, will be recorded. Dose, route, unit frequency of administration, indication, and date(s) of administration will be captured.

If participant is taking high dose biotin supplements (biotin ≥ 5,000 μg/day, found in multivitamins, biotin supplements, and supplements for hair, skin, and nail growth), a washout of 1 week before randomization is permitted.

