8.1.2 Medical History and Demographics

Medical history includes active conditions, and any medical illnesses, diagnoses, and surgeries considered clinically relevant by the Investigator.

The review will also include a detailed assessment of AD, including:

- date of symptom onset and clinical presentation
- date and method of diagnosis
- · prior and ongoing treatments, surgeries, or therapies
- · prior (or current) participation in interventional clinical trials.

Demographic information (date of birth, sex, race, ethnicity) will be recorded at Screening (as allowed by local regulations).

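### The washout rule in Section 6.8.1 is shorter than exclusions 37 and 38 allow and disagrees with itself, so a site relying on it could enroll an ineligible participant

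*Combined protocol and SAP*

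**What the plan says.** Section 6.8.1 begins by stating what a participant must satisfy to be eligible, and then covers anyone who stops a listed drug before randomization: "a washout period of the lesser of 5 half-lives or 30 days is required". The list has three entries: investigational products, anticoagulants, and moderate or strong CYP3A4 and CYP2C19 inhibitors. The first entry names anti-tau antisense or gene therapy, anti-amyloid and anti-tau immunotherapy and O-GlcNAcase inhibitors as examples of investigational products for AD, and ends "or other investigational product within 8 weeks prior to randomization".

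Section 5.4.3 treats the same products differently:

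- Exclusion 37 begins "Any prior or ongoing exposure to active or passive anti-amyloid immunotherapy" and goes on to anti-tau immunotherapy, anti-tau antisense or gene therapy, and O-GlcNAcase inhibitors. It has no time limit, and the synopsis repeats it.
- Exclusion 38 covers investigational products outside those classes: "then 12 weeks or 5 half-lives (whichever is longer) must have passed prior to randomization".
- Exclusion 41 reads "Prior use of a moderate or strong inhibitor of CYP3A4 within a period of 5 half-lives of randomization". Exclusion 42 does the same for CYP2C19. Neither has a cap in days.

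Section 5.4 introduces its list with "An individual who meets any of the following criteria will be excluded from participation in this trial". Sections 5.2 and 5.6 rule out waivers, and 5.6 ties the eligibility decision to Sections 5.3 and 5.4. No text says that 5.4 overrides 6.8.1.

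**The concern.** One rule takes the lesser of two intervals and the other takes the longer, for the same products and the same purpose. Because 6.8.1 is worded as a condition of eligibility, a coordinator checking whether a recently stopped drug has washed out could reasonably stop reading there.

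The routine medication review would not necessarily expose the mistake. Section 6.8.2 says that products "taken during the 30 days prior to Day 1 will be reviewed and recorded as prior medications", so an investigational product stopped 31 to 84 days before Day 1 falls outside it. The site would then depend on the history in Section 8.1.2, which asks about earlier treatments and "prior (or current) participation in interventional clinical trials". Even a site that learns of such a product could consult 6.8.1 and conclude that the washout is complete.

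The key secondary endpoints are CSF pTau217, CSF total tau and plasma pTau217, analyzed in the mITT set (Section 9.3). Section 9.1.1 puts anyone who took a single dose in that set, so a participant enrolled in error is not removed from the analysis. Section 9.10 likens the assumed 20% difference from placebo to that documented after 24 weeks of amyloid-lowering therapy. By the protocol's own account, then, one of the classes barred by exclusion 37 can change these biomarkers by about as much as the trial hopes to detect.

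**Working it through.** The point rests on wording, and the plan gives no figure to reproduce. The rules can be compared in days. Let *h* be a product's half-life in days. The documents give no half-lives, so *h* is varied as an assumption.

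Inputs:

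- 6.8.1 general rule: min(5*h*, 30), so never more than 30 days
- 6.8.1 first bullet: 8 weeks = 8 × 7 = 56 days
- Exclusion 38: max(12 × 7, 5*h*) = max(84, 5*h*), so never less than 84 days
- Exclusion 37: no interval restores eligibility
- Exclusions 41 and 42: 5*h*

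**Investigational products under exclusion 38**

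| *h* (days) | 6.8.1 general rule | 6.8.1 bullet | Exclusion 38 | Shortfall of general rule | Shortfall of bullet |
|---|---|---|---|---|---|
| 1 | 5 | 56 | 84 | 79 | 28 |
| 3 | 15 | 56 | 84 | 69 | 28 |
| 6 | 30 | 56 | 84 | 54 | 28 |
| 16.8 | 30 | 56 | 84 | 54 | 28 |
| 20 | 30 | 56 | 100 | 70 | 44 |
| 30 | 30 | 56 | 150 | 120 | 94 |

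The general rule reaches its 30-day ceiling at *h* = 6. Exclusion 38 leaves its 84-day floor only above *h* = 84/5 = 16.8. Between those values the shortfall is at its minimum, 84 − 30 = 54 days. The bullet's smallest shortfall is 84 − 56 = 28 days.

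**Within 6.8.1.** The bullet exceeds the general rule by 56 − min(5*h*, 30), which is at least 56 − 30 = 26 days.

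**Exclusion 37 classes.** Exclusion 37 says never, while 6.8.1 names the same classes in a list to which a washout of at most 30 days applies. The 8-week phrase could be read as attaching only to other investigational products. On that reading the general washout still reaches the exclusion 37 classes, and the 8-week versus 12-week mismatch for other products is untouched.

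**CYP inhibitors.** The gap is 5*h* − min(30, 5*h*). It is 0 for *h* up to 6; at assumed half-lives of 7 and 10 days it is 35 − 30 = 5 and 50 − 30 = 20 days. The documents do not show that any listed inhibitor has a half-life above 6 days.

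**Reach of the medication review.** Of the 84-day minimum in exclusion 38, 84 − 30 = 54 days lie outside the 30-day look-back.

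**Share of an arm.** One participant is 1/26 = 3.8%.

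**The case against.** The best reply is that eligibility is already settled elsewhere. Anyone meeting any exclusion is out, waivers are ruled out, and the bar on the exclusion 37 classes appears in both the synopsis and 5.4.3. If the rules are read cumulatively the strictest governs, and a shorter interval in 6.8.1 admits nobody. That stands as a statement of who is eligible. It does not make 6.8.1 correct, and nothing in that section tells the reader to look for a stricter rule.

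A second reply is that the general washout is tied to drugs taken daily over the long term, which fits CYP inhibitors and anticoagulants better than infusions or gene therapy, and that the 8-week phrase is a specific rule displacing the general one. This is a possible reading, and it softens the charge of self-contradiction. But the washout sentence refers to the whole list, an oral O-GlcNAcase inhibitor taken daily fits even the narrow reading, and 8 weeks still is not 12.

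A third reply is that the route to error is narrow. The history in 8.1.2 has no time limit, the criteria are reviewed at Tier 3 (Table 1) and again on Day 1 (Table 2), and Section 8.1 requires the Investigator to confirm eligibility before randomization. The Per Protocol set also removes major entry violations. These safeguards lower the risk. They do not remove it, because each relies on the site applying 5.4.3 rather than 6.8.1, and the Per Protocol set is not the one assigned to the key secondary analysis.

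The CYP mismatch is tidying only. The 3.8% is the share of one hypothetical participant; it estimates neither bias nor the chance of an error.

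**Conclusion.** The concern holds. Section 6.8.1 states a washout that the protocol's own exclusion criteria show to be wrong. For exclusion 38 products, the minimum shortfalls of 54 days (general rule) and 28 days (8-week bullet) apply at every half-life and need no assumption about the drug. For exclusion 37 classes no washout of any length is acceptable. The minimum 26-day disagreement inside 6.8.1 assumes that the general washout sentence covers everything in the list, which is its plain meaning.

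The consequence is limited to a risk of site error. Enrolling someone on 6.8.1 alone would be a protocol deviation, not a permitted entry. How often this would happen, and how far earlier exposure would carry over into change from baseline, cannot be worked out from the documents. Sample size, power and alpha are unaffected. It should be corrected because it is an operative eligibility rule, the error is certain, and the remedy is cheap.

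**What to change.** In Section 6.8.1, remove the 30-day cap and the 8-week window for the classes that 5.4.3 already covers, and restate the 5.4.3 rules there:

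- Anti-amyloid or anti-tau immunotherapy, anti-tau antisense or gene therapy, O-GlcNAcase inhibitors: no exposure at any time before randomization.
- Any other investigational product: the longer of 12 weeks or 5 half-lives before randomization.
- Moderate or strong CYP3A4 or CYP2C19 inhibitors: 5 half-lives before randomization, without a cap.

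Keep the rest of the section as the list of drugs prohibited during the DB Intervention Period. The cost is wording in the next protocol amendment. Procedures, sample size and analysis do not change.

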6.8.2 Permitted Concomitant Therapy

Concomitant therapy, particularly medications that could potentially affect cognition, should be maintained at stable doses throughout the trial, unless a change is medically necessary.

Medications (investigational, prescription, over the counter, and herbal) and nutritional supplements taken during the 30 days prior to Day 1 will be reviewed and recorded as prior medications.

All concomitant medications taken during the trial, and any changes since the previous visit, will be recorded. Dose, route, unit frequency of administration, indication, and date(s) of administration will be captured.

If participant is taking high dose biotin supplements (biotin ≥ 5,000 μg/day, found in multivitamins, biotin supplements, and supplements for hair, skin, and nail growth), a washout of 1 week before randomization is permitted.

6.8.3 Rescue Therapy

Not applicable.

6.8.4 Additional Protocol-designated Products – Positron Emission Tomography Imaging Radioligands

44 Confidential

7 DISCONTINUATION OF INTERVENTION AND PARTICIPANT WITHDRAWAL

7.1 Discontinuation of Trial Intervention

7.1.1 Criteria for Permanent Discontinuation of Trial Intervention

The Investigator and Sponsor have the right to remove participants from the trial. The Sponsor also reserves the right to discontinue participation of an individual participant.

Clinical judgement

Trial intervention may be discontinued, and participants may be removed from the trial for the following reasons:

- Occurrence of an AE or SAE that precludes further participation
- Any condition that, in the judgment of the Investigator or Sponsor, might place the participant at risk or invalidate the trial
- At the request of the participant, Investigator, or Sponsor, for administrative or other reasons
- Protocol deviation or noncompliance.

Hepatic event or liver test abnormality

Participants who are discontinued from IMP due to a hepatic event or liver test abnormality should have additional hepatic safety data collected and recorded in the eCRF as deemed necessary by Investigator to accurately follow event until resolution or baseline return.

Discontinuation of IMP for a liver test abnormality should occur when a participant meets any of the following conditions:

- ALT or AST > 8 × ULN
- ALT or AST > 5 × ULN for more than 2 weeks
- ALT or AST > 3 × ULN and TBL > 2 × ULN or INR > 1.5
- ALT or AST > 3 × ULN with the appearance of fatigue, nausea, vomiting, right upper quadrant pain or tenderness, fever, rash, and/or eosinophilia (>5%)
- ALP > 3 × ULN
- ALP > 2.5 × ULN and TBL > 2 × ULN
- ALP > 2.5 × ULN with the appearance of fatigue, nausea, vomiting, right upper quadrant pain or tenderness, fever, rash, and/or eosinophilia (> 5%).

C-SSRS

In addition, IMP may be discontinued if participants:

- Answer "yes" to Question 4 or Question 5 on the "Suicidal Ideation" portion of the C-SSRS, or
- Answer "yes" to any of the suicide-related behaviors on the Suicidal Behavior portion of the C-SSRS.

A psychiatrist may assist in the decision to discontinue the participant.

ECG

If a clinically significant finding is identified (including changes from baseline in QTcF) after enrollment, the Investigator or qualified designee will determine if the participant may continue in the trial or if a change in participant management is required. Review of ECGs must be documented upon collection and any new clinically significant ECG finding should be reported as an AE. Central review of ECGs will also be performed (see Section 8.3.3.1).

Should the following events occur in an individual participant during the trial, the Investigator, in consultation with the Sponsor's Medical Monitor, will decide if study intervention should be interrupted or permanently discontinued:

- If a participant has median PR interval of 200 ms to 220 ms AND a change from baseline in PR interval of > 10% (triplicate measurements)
- If a participant has median PR interval > 220 ms (triplicate measurements).

Systemic Hypersensitivity Reactions

If the Investigator, after consultation with the Sponsor-designated Medical Monitor, determines that a systemic hypersensitivity reaction has occurred related to IMP administration, the participant should be discontinued.

Excluded Therapeutic Agent

If the participant requires treatment with an excluded therapeutic agent and temporary discontinuation cannot be met, IMP should be discontinued.

If a participant discontinues from the trial prematurely, reasonable efforts should be made to perform the Early Termination (ET) visit procedures as soon as possible, and schedule Follow-up Visit procedures 4 weeks after the last dose of ASN51.

7.1.2 Temporary Discontinuation

Drug holidays of up to 4 days (in a 12-week period) are allowed if the participant experiences an AE that necessitates a temporary discontinuation of trial intervention, based on clinical judgment of the Investigator. Consult the Medical Monitor should these events occur.

Any drug holiday (planned or medically indicated) exceeding 7 consecutive days in duration may result in discontinuation from the trial, at the discretion of the Investigator in consultation with the Sponsor Medical Monitor.

7.1.3 Rechallenge

Generally, rechallenge will not be allowed.

7.2 Participant Withdrawal from Trial

In accordance with the Declaration of Helsinki, participants have the right to withdraw from the trial at any time for any reason. The Sponsor should be notified of all participant withdrawals as soon as possible.

The primary reason for the participant's withdrawal from the study must be recorded in the participant's eCRF.

Participants must undergo an ET Visit unless withdrawal is due to death or withdrawal of consent.

7.3 Lost to Follow-up

If a participant misses one or more scheduled visits, site personnel will perform the following prior to discontinuation as lost to follow up:

- Contact the participant to reschedule the missed visit and counsel the participant on the importance of safety monitoring
- A minimum of 3 documented attempts to contact the participant (via telephone and written or electronic communication). These contact attempts should be documented in the participant's medical record
- Should the participant continue to be unreachable, that participant will be considered to have withdrawn from the study with a primary reason of lost to follow-up.

7.4 Trial Stopping Rules

Should any of following events occur, the SRC, Sponsor, and Coordinating Investigator (along with involved Investigator(s)) will convene on *ad hoc* basis (not to exceed 5 business days after knowledge of the event):

- Death of any participant within 28 days of receipt of IMP unless inextricably related to an alternative cause
- Two or more participants in a group show a 2nd degree AV block, or Mobitz type 2 confirmed with 2 consecutive ECGs, or 3rd degree AV block

- Hy's law is met for one participant, requiring all the following:
 - ALT or AST > 3 × ULN
 - o TBL > 2 × ULN
 - ALP < 2 × ULN
 - No other obvious reason for the liver injury, such as viral hepatitis, alcohol use, or another hepatotoxic drug
- AEs occurring in the same System Organ Class (SOC; irrespective of severity or seriousness) leading to discontinuation of trial intervention in 3 or more participants.

All available information regarding the event(s) will be evaluated. Based on reasonable clinical judgment, a decision will be made whether or not the event(s) needs to be further characterized with respect to progression and reversibility; and whether it is reasonable to alter ongoing treatment (criteria/monitoring), recommend a pause in further enrollment, or recommend stopping the trial.

